## 1. PROTOCOL SUMMARY

Study Title	Deep Learning-Based Intraoperative Dual-Tracer Video Analysis of Sentinel Lymph Node Mapping for Metastasis Prediction in cN0 Papillary Thyroid Carcinoma
Study Type	Prospective Observational Cohort Study
Registry Number	NCT06871956
Study Population	Adults ( $\geq 18$ years) with clinically node-negative papillary thyroid carcinoma (cN0-PTC)
Sample Size	336 participants (112 per group $\times$ 3 groups)
Study Groups	1) ICG Group, 2) CNs Group, 3) ICG+CNs (Dual-Tracer) Group
Primary Outcomes	SLN detection rate, SLNM status, SeLNM, NsLNM
Study Duration	April 2024 - October 2024 (enrollment); 12 months follow-up
Study Sites	The First Affiliated Hospital of Chongqing Medical University, Chongqing, China
Principal Investigator	[name], MD, PhD

## 2. INTRODUCTION AND BACKGROUND

### 2.1 Disease Background

Papillary thyroid carcinoma (PTC) is among the fastest-growing endocrine malignancies worldwide. Despite excellent overall prognosis, lymph node metastasis (LNM) remains a central clinical challenge. Even in patients classified as clinically node-negative (cN0) by routine preoperative ultrasonography and cross-sectional imaging, 30% to 80% may harbor occult LNM that is not detected before surgery.

This staging gap creates a significant clinical dilemma: extensive lymph node dissection may increase morbidity (including hypoparathyroidism and recurrent laryngeal nerve injury), while limited dissection risks leaving metastatic disease behind, potentially contributing to disease recurrence. A reliable intraoperative strategy that improves detection and risk stratification of occult nodal disease is urgently needed to support patient-specific, precision lymph node management in PTC.

### 2.2 Sentinel Lymph Node Mapping in PTC

Sentinel lymph node (SLN) mapping has been investigated to tailor the extent of lymph node dissection by identifying first-echelon nodes along patient-specific thyroid lymphatic drainage. The concept is based on the principle that if cancer spreads through the lymphatic system, it will reach these sentinel nodes first.

However, SLN-based approaches in PTC have shown variable performance, partly because thyroid lymphatic pathways are complex and difficult to visualize *in vivo*. No single tracer provides both precise SLN localization and robust information on lymphatic flow dynamics:

- Radiotracer methods can be accurate but require nuclear-medicine infrastructure, increase cost, and raise concerns about workflow and contamination.
- Superparamagnetic iron oxide techniques depend on specialized equipment and can be affected by intraoperative signal interference.
- Carbon nanoparticles (CNs) provide durable visual staining yet offer limited dynamic information.
- Indocyanine green (ICG) enables near-infrared fluorescence imaging of lymphatic flow but can diffuse, suffer from background contamination, and has limited penetration depth.

### 2.3 Rationale for Dual-Tracer Approach

To address these limitations, we employ a dual-tracer strategy combining CNs and ICG, leveraging sustained visual staining with spatiotemporal near-infrared fluorescence (NIRF) signals during intraoperative SLN mapping. This combination offers several advantages:

- ICG enables real-time, dynamic monitoring of lymphatic flow and aggregation, allowing complete visualization of lymphatic drainage pathways.
- CNs provide long-lasting black staining that facilitates identification and resection of lymph nodes.
- The combined approach compensates for individual tracer limitations and improves sentinel node identification accuracy.

## **2.4 Role of Deep Learning**

Deep learning (DL) is well suited to extract high-dimensional spatiotemporal patterns from surgical videos and to integrate them with clinicopathological variables, potentially revealing predictive signals beyond what is apparent to the human eye. By applying explainable artificial intelligence (XAI) methods such as SHAP (SHapley Additive exPlanations), we can identify influential features and provide interpretable outputs to support intraoperative decision-making.

## 3. STUDY OBJECTIVES AND HYPOTHESES

### 3.1 Primary Objectives

1. To compare the sentinel lymph node detection rate among three tracer methods: ICG alone, CNs alone, and ICG+CNs dual-tracer combination.
2. To evaluate and compare the diagnostic performance (sensitivity, specificity, PPV, NPV) of each tracer method for predicting central lymph node metastasis.
3. To develop and validate deep learning models using multimodal features (spatiotemporal video features + clinical variables) for predicting second-echelon lymph node metastasis (SeLNM) and non-sentinel lymph node metastasis (NsLNM).

### 3.2 Secondary Objectives

- To identify the optimal deep learning architecture for lymph node metastasis prediction.
- To determine the most important predictive features using SHAP analysis.
- To assess the clinical utility of AI-assisted intraoperative decision support.
- To evaluate safety outcomes including surgical complications and tracer-related adverse events.

### 3.3 Hypotheses

Primary Hypothesis: The ICG+CNs dual-tracer combination will demonstrate superior sentinel lymph node detection rate compared to either tracer alone.

Secondary Hypothesis: Time-series fluorescence-flow signatures, combined with spatial structural cues and clinicopathological factors, will improve prediction of SeLNM and NsLNM compared with SLN status alone.

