## 8. DATA COLLECTION AND MANAGEMENT

### 8.1 Clinical Data Collection

A total of 32 clinical variables will be collected for each participant:

Demographics (3 variables): Age, sex, body mass index (BMI)

Ultrasound features (9 variables): Tumor size, tumor margin, calcification pattern, aspect ratio, internal echoes, homogeneity, intratumoral blood flow, peritumoral blood flow, TI-RADS classification

Pathological features (10 variables): Tumor location, laterality, multifocality, capsular invasion, extrathyroidal extension (ETE), Hashimoto's thyroiditis, T stage, SLN location, SLN metastasis status, number of positive SLNs

Genetic data: BRAF mutation status and other relevant mutations

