## 9.4 Deep Learning Model Development

### 9.4.1 Model Architectures

Nine deep learning architectures will be developed and compared:

- Convolutional Neural Network (CNN)
- Long Short-Term Memory (LSTM)
- CNN + LSTM hybrid
- CNN + LSTM + Attention
- Transformer
- Crossformer
- 3D-CNN

- LSTM + Transformer hybrid
- LSTM + Crossformer hybrid

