### 9.6 Model Comparison

- DeLong test for comparing AUC values between models
- Probability-based model ranking approach (PMRA)
- Win-probability heatmaps
- Wald test p-value comparisons
- Decision curve analysis for clinical utility
- Calibration curves for reliability assessment
- Learning curves for overfitting assessment

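### The secondary hypothesis compares a video-plus-clinical model with SLN status alone, so a positive result could not show that the video adds anything beyond routine clinical variables

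*Combined protocol and SAP*

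**What the plan says.** - **Hypothesis (3.3).** The predictor set under test is a bundle: "Time-series fluorescence-flow signatures, combined with spatial structural cues and clinicopathological factors". The claim is that it "will improve prediction of SeLNM and NsLNM compared with SLN status alone". No other comparator is named.
- **Objective (3.1, item 3).** The models are built on "multimodal features (spatiotemporal video features + clinical variables", together.
- **Clinical inputs (8.1).** "A total of 32 clinical variables will be collected for each participant". The list includes "SLN metastasis status, number of positive SLNs", so the comparator is itself one of the listed clinical variables. The same list holds tumour size, T stage, extrathyroidal extension, multifocality, capsular invasion and BRAF status.
- **Models (9.4.1).** "Nine deep learning architectures will be developed and compared". They are distinguished by network type. The section does not state the input set of any of them.
- **Comparison (9.6).** "DeLong test for comparing AUC values between models" heads the list, with no reference model named. Even the contrast with SLN status alone is not written out there.
- **Interpretation (9.7).** SHAP ranks feature contributions, with no decision rule attached.

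**The concern.** The tested model differs from its comparator in two ways at once: it adds video, and it adds many clinical variables. Several of those could improve on one binary predictor without any video. The stated contrast can therefore favour the hypothesis when the video carries no signal.

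The study title and section 2.4 present video as the source of new predictive information. Video is also the laborious component: a recording of at least five minutes (6.4) and manual region marking by two senior surgeons (8.2). Whether it adds to data already in the chart is the practical question, and the stated contrast does not address it.

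**Working it through.** **Inputs from the documents.** 112 patients in the dual-tracer group (4.2); 10-fold stratified cross-validation (9.4.3); two-sided 0.05 (9.9); DeLong test (9.6); features reduced to 32 dimensions (8.3). The documents give no AUC, event rate, effect size or power for the secondary hypothesis, so there is no planned figure to reproduce. Every effect size below is an assumption.

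**Step 1: what the contrast estimates.** Let (a) be SLN status alone, (b) SLN status plus clinical variables without video, and (c) the full model. Then

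AUC(c) − AUC(a) = [AUC(c) − AUC(b)] + [AUC(b) − AUC(a)].

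The first bracket is the video gain and the second is the clinical gain. Section 3.3 names only the sum. Since (b) is specified nowhere, the plan does not estimate the brackets separately.

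**Step 2: upper bound with useless video.** Assume 45% SLN-positive, log-odds ratio 1.8 for SLN status, outcome prevalence about 27–29%, one clinical score with log-odds 0.5, 0.75 or 1.0 per SD, and zero video information. Give the DeLong test the true linear predictor, so nothing is estimated. The clinical gain in AUC runs from 0.76 − 0.70 = 0.06 at the weakest score to 0.80 − 0.68 = 0.12 at the strongest. Improvement over SLN status alone is declared in 48% / 73% / 84% of cohorts. Repeats gave 49% / 72% / 85% and 51% / 73% / 84%.

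**Step 3: the same signal, fitted.** Ridge logistic models in 10-fold cross-validation, video still without signal. Ranges are across repeats that differed in the number of noise video inputs (none to five in the first two rows) and in fitting details.

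| Inputs | 0.5 | 0.75 | 1.0 |
|---|---|---|---|
| True predictor (Step 2) | 48% | 73% | 84% |
| One fitted clinical score | 4–18% | 17–47% | 46–79% |
| Same signal over four variables | 1–9% | 8–25% | 23–56% |
| With 32 noise video features | 0–1% | 0–2% | 0–7% |

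The upper ends of the second and third rows come from fits with no noise video inputs (stratified folds, ridge penalty 5, 1,000 cohorts, outcome rate 29%).

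**Step 4: stronger clinical signal, and the contrast that isolates video.** Assume 50% SLN-positive, SLN log-odds 1.5, outcome rate about 41–44%, and four independent clinical variables with log-odds 0.5, 0.75 or 1.0 each. Combined, that is √4 × 0.5 = 1.0, then 1.5 and 2.0 per SD; the last two lie beyond the Step 2 range. With 300 runs per setting, (c) significantly beat (a) in 42% / 89% / 99% of runs with 5 noise video features, and in 7% / 44% / 74% with 32. It significantly beat (b) in at most 0.3%.

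One setting shows the problem plainly. With variables at 1.0 each and 32 noise features, mean AUCs were (a) 0.611, (b) 0.854 and (c) 0.770. The stated contrast is 0.770 − 0.611 = +0.159. The video contrast is 0.770 − 0.854 = −0.084. Here adding video made prediction worse, yet the stated contrast was significant in favour of the combined model in 74% of runs.

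**The case against.** The strongest reply is that 3.3 credits a combination, and for that claim SLN status alone is a legitimate reference: it is what the surgeon has from the sentinel node. Objective 3 is to develop and validate multimodal models, not to isolate video. This stands, and (a) should be kept.

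A reader might infer that a clinical gain would be credited to video. No passage says so; that would be a matter of how results are later interpreted. A reader might also infer that a clinical-only model has been ruled out. It has not: 9.4.1 gives no input sets and 9.6 names no reference, so the comparator is unspecified.

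SHAP could show clinical features dominating. It is a useful description, but it ranks contributions inside a fitted model. It neither estimates nor tests the out-of-sample gain from adding video.

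Finally, the simulated rates do not describe the planned networks. Tuned deep models, or picking the best of nine, could behave differently from ridge regression. This also stands. The rates show direction and a range, not a forecast.

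**Conclusion.** The concern holds in a limited form. As specified, a positive result would support the combined model over SLN status, but could not show that fluorescence-flow video adds to routine clinical variables. That follows from the choice of comparator and needs no assumed effect size.

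Its frequency is uncertain. The 48% to 84% figures are an upper bound for a perfectly known clinical score of log-odds 0.5 to 1.0 per SD. Cross-validated fitting lowered the rate in every variant of those settings, to a few per cent or less in most cases with 32 noise features. Only clinical effects beyond that range gave higher rates. Reading the upper figures as the expected false-support rate for this study would go too far.

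So would saying that the trial cannot answer its own question. The primary hypothesis concerns detection rate across 336 participants and is untouched, and the secondary hypothesis as worded can be tested. What is missing is an inexpensive comparison that would make any claim about video interpretable.

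**What to change.** In 9.6, prespecify three models on the same dual-tracer patients and the same folds, separately for SeLNM and NsLNM:

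- (a) SLN status alone;
- (b) SLN status plus the same clinical variables as the full model, with no video;
- (c) the full model.

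Rest any claim about video on (c) minus (b) in AUC and Brier score, with a patient-level bootstrap confidence interval and net benefit as support. Keep (c) minus (a) as the test of the combination, and write it into 9.6. Reword 3.3 so that the combination claim and the video claim are separate. Name the clinical variables entering (b) and (c): 8.1 states 32 but itemises 3 + 9 + 10 = 22 plus genetic data.

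I would not add reporting within SLN strata. Under the Step 2 assumptions, about 112 × 0.55 ≈ 62 patients are SLN-negative and roughly 15% have the outcome. That is about 9 events, too few for a useful AUC or net benefit.

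The cost is SAP wording and extra model fits: two reference models for each of two outcomes, so four per fold. No patients, data or procedures are added, since 6.3 states that the predictions are retrospective and do not affect surgery. The real downside is a probably smaller headline gain.

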## 4. STUDY DESIGN

### 4.1 Study Type and Design

This is a prospective, single-center, three-arm observational cohort study. Participants will be allocated to one of three groups based on the sentinel lymph node mapping technique used during their thyroid surgery.

### 4.2 Study Groups

Group 1 - ICG Group (n=112): Sentinel lymph node mapping using indocyanine green alone with near-infrared fluorescence imaging.

Group 2 - CNs Group (n=112): Sentinel lymph node mapping using carbon nanoparticles alone with visual identification.

Group 3 - ICG+CNs Group (n=112): Sentinel lymph node mapping using combined dual-tracer technique with both NIRF imaging and visual identification. This group will also undergo deep learning video analysis.

### 4.3 Study Timeline

- Ethics Approval: October 16, 2023
- Enrollment Period: April 2024 - October 2024
- Follow-up Period: 12 months post-surgery
- Data Analysis and Reporting: After completion of enrollment

### 4.4 Study Setting

The study will be conducted at the Department of Breast and Thyroid Surgery, The First Affiliated Hospital of Chongqing Medical University, Chongqing, China. This is a tertiary referral center with expertise in thyroid cancer surgery and advanced surgical imaging techniques.

## 5. STUDY POPULATION

### 5.1 Target Population

Adults diagnosed with clinically node-negative papillary thyroid carcinoma (cN0-PTC) who are scheduled for surgical treatment.

### 5.2 Inclusion Criteria

1. Age  $\geq$ 18 years at the time of enrollment
2. Histologically confirmed papillary thyroid carcinoma by preoperative fine-needle aspiration biopsy
3. Clinically node-negative (cN0) status confirmed by preoperative imaging (ultrasound and/or cross-sectional imaging showing no evidence of lymph node metastasis)
4. Scheduled to undergo thyroid surgery with simultaneous central lymph node dissection
5. Willing and able to provide written informed consent
6. Complete preoperative clinical data available

### 5.3 Exclusion Criteria

1. History of previous neck surgery
2. History of external beam radiotherapy to the head and neck region
3. Diagnosis of thyroid malignancy other than papillary thyroid carcinoma
4. Known allergy or hypersensitivity to indocyanine green (ICG), iodine, or carbon nanoparticles
5. Severe hepatic insufficiency (ICG is metabolized by the liver)
6. Pregnancy or breastfeeding
7. Incomplete medical records or missing essential preoperative data
8. Refusal to undergo dual-tracer imaging procedure
9. Participation in another interventional clinical trial that may interfere with the current study

## 6. STUDY INTERVENTIONS AND PROCEDURES

### 6.1 Preoperative Assessment

All participants will undergo standard preoperative evaluation including:

- Complete medical history and physical examination
- Thyroid ultrasound with detailed lymph node assessment
- Fine-needle aspiration biopsy for cytological confirmation
- Genetic testing for common mutations (BRAF, etc.)
- Standard laboratory tests (complete blood count, thyroid function, liver function)
- Preoperative photography and documentation

### 6.2 Tracer Preparation and Administration

#### 6.2.1 ICG Group

- Preparation: ICG powder (25 mg) dissolved in 10 ml sterile water to achieve concentration of 2.5 mg/ml
- Administration: 0.2 ml of ICG solution injected at multiple points around the thyroid tumor under real-time ultrasound guidance
- Visualization: Near-infrared fluorescence imaging system (excitation 750-800 nm, emission 820 nm)

#### 6.2.2 CNs Group

- Preparation: Carbon nanoparticle suspension at commercial concentration (50 mg/ml)
- Administration: 0.2 ml of CNs suspension injected at multiple points around the thyroid tumor under ultrasound guidance
- Visualization: Direct visual identification of black-stained lymph nodes

#### 6.2.3 ICG+CNs Group (Dual-Tracer)

- Preparation: 0.1 ml ICG solution (2.5 mg/ml) mixed with 0.1 ml CNs suspension (50 mg/ml) to form 0.2 ml dual-tracer composite
- Administration: Multi-point stereotactic injection under ultrasound guidance
- Visualization: Combined NIRF imaging and visual black staining identification
- Video recording: Minimum 5 minutes at 1920×1080 resolution, 29.97 fps

### 6.3 Surgical Procedure

All participants will undergo standard thyroid surgery following institutional protocols:

- Identification and separate submission of sentinel lymph node for pathological examination
- Ipsilateral thyroid lobectomy or total thyroidectomy as clinically indicated
- Ipsilateral central lymph node dissection (Level VI)
- Intraoperative frozen section analysis of sentinel lymph node

- Extended dissection (lateral compartment, contralateral central) based on frozen section findings

Surgical decisions will follow standard protocols and will NOT be influenced by deep learning predictions (which are performed retrospectively).

#### **6.4 Video Recording Protocol (ICG+CNs Group)**

- Equipment: Near-infrared fluorescence imaging system (Mingde Pharmaceutical, Henan, China)
- Recording parameters: 1920×1080 resolution, 29.97 frames per second
- Duration: From tracer injection until secondary lymph node fluorescence disappears (minimum 5 minutes)
- Content: Complete SLN visualization process including lymphatic flow dynamics
- Storage: Digital files exported via USB for subsequent analysis

#### **6.5 Pathological Examination**

- Intraoperative frozen section: Sentinel lymph node and representative lymph nodes
- Postoperative formalin-fixed paraffin-embedded (FFPE) processing for definitive diagnosis
- Independent review by three pathologists
- Final diagnosis based on paraffin section results (gold standard)
- Documentation of metastasis location, size, and extent

## 7. OUTCOME MEASURES

### 7.1 Primary Outcomes

#### 7.1.1 Sentinel Lymph Node Detection Rate

Definition: Proportion of participants with successfully identified sentinel lymph nodes using each tracer method.

Measurement: Number with identified SLN / Total number in group  $\times 100\%$

Time Frame: Intraoperative (Day 0)

#### 7.1.2 Sentinel Lymph Node Metastasis (SLNM) Status

Definition: Presence or absence of cancer metastasis in the sentinel lymph node.

Classification: Positive (macrometastasis or micrometastasis) or Negative

Gold Standard: Final histopathological examination (paraffin section)

Time Frame: Within 7 days after surgery

#### 7.1.3 Second-Echelon Lymph Node Metastasis (SeLNM)

Definition: Presence or absence of cancer metastasis in second-echelon lymph nodes (beyond the sentinel node in the drainage pathway).

Primary prediction target for deep learning models in ICG+CNs group.

Time Frame: Within 7 days after surgery

#### 7.1.4 Non-Sentinel Lymph Node Metastasis (NsLNM)

Definition: Presence or absence of cancer metastasis in any lymph node other than the sentinel lymph node.

Includes central and lateral compartment nodes (when dissected).

Time Frame: Within 7 days after surgery

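### NsLNM is searched for in a field that depends partly on SLN status, and section 9 never puts participants on a common field

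*Combined protocol and SAP*

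**What the plan says.** The outcome (7.1.4) is "Presence or absence of cancer metastasis in any lymph node other than the sentinel lymph node", followed by "Includes central and lateral compartment nodes (when dissected". The protocol summary lists NsLNM among the primary outcomes.

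The surgery (6.3) gives everyone "Ipsilateral central lymph node dissection (Level VI" side only. Beyond that comes "Extended dissection (lateral compartment, contralateral central) based on frozen section findings". The frozen section covers, in 6.5, "Intraoperative frozen section: Sentinel lymph node and representative lymph nodes".

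The third primary objective (3.1) is to build models from "multimodal features (spatiotemporal video features + clinical variables) for predicting second-echelon lymph node metastasis (SeLNM) and non-sentinel lymph node metastasis (NsLNM". The clinical variables in 8.1 include "T stage, SLN location, SLN metastasis status, number of positive SLNs". The secondary hypothesis (3.3) is that the combined features "will improve prediction of SeLNM and NsLNM compared with SLN status alone".

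Section 9 contains no NsLNM analysis on a common field, no stratification or adjustment by extent of dissection, and no rule for coding compartments that were not dissected. Section 9.8 plans complete-case analysis for primary outcomes and unspecified sensitivity analyses for missing data.

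**The concern.** The definition promises any non-sentinel node, but delivers whichever nodes the surgeon had reason to remove. One of those reasons is the SLN frozen section. A participant with a negative SLN and no other positive frozen node has no stated trigger for extension, and is recorded NsLNM-negative with the lateral and contralateral central compartments unexamined. The same participant with a positive SLN could be extended and recorded positive.

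This is differential verification. The variable that helps decide where the outcome is sought is also a predictor of it and the benchmark the model must beat. Two results are exposed:

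- The share of SLN-negative participants reported without non-sentinel disease means only that none was found in the dissected field. Section 2.1 names residual metastasis as the danger of limited dissection, so a reader may well take that share to mean more.
- The SLN–NsLNM association, and with it the weight of SLN status in the model and the SHAP ranking, is partly a product of the extension rule.

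**Working it through.** The plan gives no figure for this point, so there is none to reproduce. The check has a textual part and an illustration.

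**Does the plan handle it?** An undissected compartment is not a missing value under 7.1.4: the participant still has an NsLNM status, namely negative. The complete-case rule in 9.8 therefore does not act on it. Extension after a positive representative node does not even things out, because a positive non-sentinel node already makes that participant NsLNM-positive. Section 6.5 asks for metastasis location to be documented, and 7.2 counts total nodes retrieved. Neither gives the compartments that were dissected and found clean. That item is not named in section 7 or among the 3 + 9 + 10 = 22 variables itemised in 8.1 (32 announced, with genetic data uncounted).

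**Inputs.** The dual-tracer group has n = 112 (4.2). Taking prevalence 50% and sensitivity 85% from 5.4, 112 × 0.50 × 0.85 = 47.6, so about 48 are SLN-positive and 64 SLN-negative. Everything else is assumed, because the documents give no rates:

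- q = probability of non-sentinel metastasis in ipsilateral Level VI: q1 = 0.50 if SLN-positive, q0 = 0.15 if SLN-negative.
- e = probability of metastasis only outside that field, given none inside it: 5%, 10% or 20%.
- x = share of SLN-positive participants extended.
- No label-changing extension in SLN-negative participants.

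**Formulas.** Full ascertainment: q + (1 − q)e. Recorded if SLN-positive: q1 + (1 − q1)·e·x. Recorded if SLN-negative: q0. Level VI only: q1 and q0.

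**Equal e, x = 1.** For e = 10%, full ascertainment gives 0.50 + 0.50 × 0.10 = 55.0% and 0.15 + 0.85 × 0.10 = 23.5%, OR = (0.55/0.45)/(0.235/0.765) = 3.98. Recorded is 55.0% against 15.0%, OR = (0.55/0.45)/(0.15/0.85) = 6.93. Level VI only gives (0.50/0.50)/(0.15/0.85) = 5.67.

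| e | OR, full field | OR, as defined | OR, Level VI only | SLN-negative without NsLNM: recorded / full | Unseen disease among 64 | Labels changed by extension among 48 |
|---|---|---|---|---|---|---|
| 5% | 4.64 | 6.26 | 5.67 | 85.0% / 80.8% | 2.7 | 1.2 |
| 10% | 3.98 | 6.93 | 5.67 | 85.0% / 76.5% | 5.4 | 2.4 |
| 20% | 3.19 | 8.50 | 5.67 | 85.0% / 68.0% | 10.9 | 4.8 |

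The last two columns are 64 × 0.85 × e and 48 × 0.50 × e.

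**Null case.** Set q1 = q0 = 0.30, so that SLN status carries no information and the true OR is 1.00. As defined, e = 5%, 10% and 20% give OR 1.18, 1.37 and 1.83 with x = 1, and 1.09, 1.18 and 1.37 with x = 0.5. For example, with e = 10% and x = 1: 0.30 + 0.70 × 0.10 = 0.37, and (0.37/0.63)/(0.30/0.70) = 1.37. Level VI only gives 1.00.

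**Unequal e.** Keep q1 = 0.50 and q0 = 0.15, with e = 20% if SLN-positive and 2% if SLN-negative. Full ascertainment gives 60.0% against 0.15 + 0.85 × 0.02 = 16.7%, OR 7.5. As defined, the OR is 8.5 with x = 1. With x = 0.5 it is (0.55/0.45)/(0.15/0.85) = 6.9, below the full-field value. Unseen disease falls to 64 × 0.85 × 0.02 = 1.1 participants, and the full-field share without NsLNM is 83.3%.

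**The case against.** The strongest reply has five parts.

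- **The trigger is inferred.** Section 6.3 does not state what finding leads to extension, and 6.5 lets unspecified representative nodes contribute. If extension mostly follows a positive non-sentinel node, few labels change. Any representative nodes taken outside ipsilateral Level VI would narrow the gap, and frozen section is not the same as final SLN status. This stands as a limit on size. Extension on a positive SLN is still the natural reading.
- **Equal out-of-field disease contradicts the sentinel premise.** Section 2.2 holds that spread reaches the sentinel node first, so disease only outside Level VI should be rarer when the SLN is negative. This stands. A reader might infer from the equal-e table that SLN status is bound to look too strong against full ascertainment. The unequal case shows that the documents do not support this.
- **Restricting to Level VI recovers nothing.** Every SLN-negative label stays as it is, still 85.0% in the illustration, and the restricted OR of 5.67 is not the full-field value. This also stands. The restriction changes the question to one the study can answer for everyone.
- **The limit is declared.** The words about dissection are openly in 7.1.4. But declaring the limit does not equalise the search, and section 9 makes no use of it.
- **SeLNM is the lead target.** Section 7.1.3 names SeLNM as the primary prediction target. A reader might extend the concern to it, but nothing in the documents shows that SeLNM is affected.

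**Conclusion.** The point holds as a defect in the NsLNM label. Part of the association between SLN status and NsLNM comes from where surgeons looked, and the plan has no analysis that separates this out. If only SLN-positive participants are extended and extension ever finds disease that Level VI did not, the recorded odds ratio must exceed the Level VI one, because only the SLN-positive rate rises. Against full ascertainment, neither size nor direction can be derived from the documents. In the null case with equal out-of-field disease, the rule alone gives OR 1.09 to 1.83. With such disease rarer in SLN-negative participants and half of SLN-positive participants extended, 6.9 is recorded where the full-field value is 7.5.

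Some SLN-negative participants are mislabelled against the any-node definition whenever they carry any out-of-field-only disease, but how many is unknown. A reader might also infer that the model's gain over SLN status alone (3.3) is biased in a known direction. The documents do not settle that either way.

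**What to change.** For the main NsLNM analysis and the model target, define NsLNM as metastasis in ipsilateral Level VI nodes other than the SLN, and name it so wherever it is reported. Report lateral and contralateral central metastasis separately, with the number of participants dissected in each compartment as denominator. Keep the any-node-when-dissected version as a sensitivity analysis. Add compartments dissected to 8.1, taken from operative and pathology reports, so that the restricted label and the denominators can be built. Location of metastases is already documented under 6.5.

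The cost is one reworded definition and one extracted item. No surgery changes. Events fall slightly: by 1.2, 2.4 or 4.8 of 112 in the illustration, for example 24.0 instead of 26.4 among 48 SLN-positive participants at e = 10%. The main NsLNM model would no longer speak to lateral or contralateral disease, which this study cannot verify in participants who were not extended.
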